7.2.3 SPECIMEN PREPARATION, HANDLING, STORAGE, AND SHIPPING

Refer to the study's laboratory manual for specimen preparation, handling, storage, and shipping procedures.

7.3 STUDY SCHEDULE

Visit windows (when noted) should be benchmarked relative to Visit 3 for a subject, such that subjects complete the entire study by Day 33 ± 7 days. Study visit procedures are listed in the recommended order in which they should be completed.

7.3.1 SCREENING

Screening Visit (Day -28 to -8)

- Obtain informed consent from the subject's legally authorized representative and informed assent from the subject, if applicable, prior to performing any study-related assessments.
- Assess for probable AD using NIA-AA criteria and administer the MMSE.
- Conduct the MHIS.
- Obtain medical history to determine eligibility based on inclusion/exclusion criteria.
- Collect demographic information.
- Review subject's current and prior medications.
- Collect vital signs, height, and weight.
- Perform the physical exam.
- Perform the 12-lead ECG.
- Collect blood and urine specimens for labs.
- Perform transthoracic echocardiogram.

Note: The Screening Visit may be split to allow sufficient time to complete all required procedures. AEs and concomitant medications should be recorded during split visits, if applicable.

7.3.2 BASELINE

Baseline Visit (Days -7 to -1)

- Re-review Screening assessments for eligibility.
- Review AEs and concomitant medications.
- Collect vital signs.
- Ensure the subject has had an opportunity to eat a meal or snack prior to administering cognitive and functional assessments.
- Administer cognitive and functional assessments in the following order:
 1. SIB
 2. ADCS-ADL-Severe
 3. ADCS-CGIC
 4. NPI or NPI-NH

7.3.3 RANDOMIZATION

It is recommended that subjects be randomized at the start of Visit 3, prior to receiving their first dose. However, subjects may be randomized at any time after eligibility has been confirmed but prior to receiving their first dose on Visit 3.

7.3.4 TREATMENT

The treatment period includes a total of 5 infusions during Week 1. It is anticipated that sites will infuse subjects with 5 doses over 5 days. A “grace day” is allowed in the event of unanticipated safety or health concerns during the treatment period.

Visits 3 -7 (Days 1-5)

- Perform the following procedures prior to administering study treatment:
 - Review AEs and concomitant medications.
 - Obtain samples for proteomics/epigenetics/biobanking; fasting samples preferred (**Visit 3 Only**).
 - Obtain sample for ApoE genotype testing (**Visit 3 Only**).
 - Obtain pre-infusion safety laboratory samples and assess results **prior to the next day's infusion (Visits 4, 5, and 6 Only)**. (When using an i-STAT Handheld Blood Analyzer, the blood sample(s) may be obtained on the same day as the infusion, provided that all pre-infusion safety lab results are available and interpreted prior to the subject's infusion start on Visits 5, 6, and 7.)
 - Collect urine for urinalysis (**Visit 6 Only**).
 - Measure and record the subject's weight in kilograms.
 - Perform targeted physical exam (i.e. auscultation of heart and lungs and assessment of peripheral edema) (**Visits 3, 5, and 7 Only**).
 - Perform 12-lead ECG (**Visits 3 and 5 Only**).
 - Collect pre-infusion vital signs.
- Administer study treatment and perform safety assessments per the Infusion Administration Manual.

7.3.5 FOLLOW-UP VISITS

Follow-up Visit 8 (Day 6 + 3 days)

- Review AEs and concomitant medications.
- Collect the following:
 - Vital signs and subject's weight in kilograms.
 - Blood and urine samples for safety labs (fasting samples preferred).
 - Samples for proteomics/epigenetics/biobanking (fasting samples preferred).
- Perform 12-lead ECG.
- Ensure the subject has had an opportunity to eat a meal or snack prior to administering cognitive and functional assessments.
- Administer cognitive and functional assessments in the following order:
 1. SIB
 2. ADCS-CGIC

Follow-up Visit 9 (Day 12 ± 3 days)

- Review AEs and concomitant medications.
- Collect the following:
 - Vital signs and subject's weight in kilograms.
 - Blood samples for safety labs (fasting samples preferred).
- Ensure the subject has had an opportunity to eat a meal or snack prior to administering cognitive and functional assessments.
- Administer cognitive and functional assessments in the following order:
 1. SIB
 2. ADCS-CGIC
 3. NPI or NPI-NH

7.3.6 FINAL STUDY VISIT

Visit 10, End of Study (Day 33 ± 7 days)

- Review AEs and concomitant medications.
- Collect the following:
 - Vital signs and subject's weight in kilograms.
 - Blood and urine samples for exit safety labs (fasting samples preferred).
 - Samples for proteomics/epigenetics/biobanking (fasting samples preferred).
- Perform the physical exam.
- Perform the 12-lead ECG.
- Ensure the subject has had an opportunity to eat a meal prior to administering the cognitive and functional assessments.
- Administer cognitive and functional assessments in the following order:
 1. MMSE
 2. SIB
 3. ADCS-ADL-Severe
 4. ADCS-CGIC
 5. NPI or NPI-NH

7.3.7 EARLY TERMINATION VISIT

If a subject has received at least one infusion but is terminated or terminates from the study early, the site should try to perform all assessments scheduled at the End of Study Visit.

7.3.8 SCHEDULE OF EVENTS TABLE

A tabular summary of all procedures by study visit can be found in [Section 15 Schedule of Events](#).

7.4 CONCOMITANT MEDICATIONS, TREATMENTS, AND PROCEDURES

All prescription, over-the-counter, and non-prescription medications (including herbal therapies and supplements) must be documented in the source documents and CRFs. All subjects should be maintained on the same medications at the same dosage and administration for treatment of AD throughout the entire study period, as medically feasible, with no introduction of new chronic therapies. Any changes in medications should be documented with reason for change (e.g., AE, etc.).

7.5 PROHIBITED MEDICATIONS, TREATMENTS, AND PROCEDURES

The following are prohibited:

- Concurrent participation in any other therapeutic treatment trial. If there was prior clinical trial participation, subject must have discontinued investigational agents for at least 30 days for small molecules, and 1 year for active or passive immunotherapies prior to Screening.
- Use of an anticoagulant therapy (e.g., heparin, warfarin, thrombin inhibitors, Factor Xa inhibitors). Use of antiplatelet drugs (e.g., aspirin or clopidogrel) is acceptable.
- Any drugs of the interferon class.
- Systemic corticosteroids (e.g., hydrocortisone, cortisone, betamethasone, prednisone, prednisolone, triamcinolone, dexamethasone, fludrocortisone) for longer than 5 consecutive days. Ophthalmic, topical, intra-articular, and inhaled steroids are allowed.

8 ASSESSMENT OF SAFETY

Assessment of safety will be conducted by blinded study personnel except in extraordinary circumstances where knowledge of whether GRF6019 or placebo was received by a subject is essential. Any instances of unblinding will be managed as indicated in [Section 10.6.3 Breaking the Study Blind/Subject Code](#).

8.1 SPECIFICATION OF SAFETY PARAMETERS

8.1.1 DEFINITION OF ADVERSE EVENTS (AE)

Per 21 CFR 312.32(a) an AE is any untoward (unfavorable, harmful, or pathologic) medical occurrence in a subject administered a medicinal (investigational) product even if the event does not necessarily have a causal relationship with this treatment.

An AE can therefore be any unfavorable and unintended sign (including an abnormal laboratory finding that is deemed clinically significant), symptom, or disease temporally associated with the use of a medicinal

(investigational) product whether or not related to the medicinal (investigational) product.

An AE does include any:

- Exacerbation of a pre-existing illness.
- Subjective or objective symptoms spontaneously offered by the subject or the subject's caregiver and/or observed by the investigator or study staff.
- Increase in frequency or intensity of a pre-existing episodic event or condition.
- Condition detected or diagnosed after study drug administration even though it may have been present prior to the start of the study (unless it can be demonstrated by medical record review that the onset of the event preceded the date/time of Informed Consent).
- Continuous persistent disease or symptoms present at baseline that worsen following the start of the study.
- Symptoms associated with disease not previously reported by the subject/caregiver.
- Untoward medical occurrences considered by the investigator to be related to study-mandated procedures.
- Abnormal assessments (e.g., change on physical examination, ECG findings), if they represent a clinically significant finding, that were not present at baseline or worsened during the course of the study.
- Laboratory test abnormalities, if they represent a clinically significant finding, symptomatic or not, which were not present at baseline or worsened during the course of the study.

An AE DOES NOT include a/an:

- Elective medical or surgical procedure (e.g., surgery, endoscopy, tooth extraction, transfusion).
- Pre-existing diseases or conditions present or detected at the start of the study that do not worsen.
- Situations where an untoward medical occurrence has not occurred (e.g., hospitalization for cosmetic elective surgery, social and/or convenience admissions).
- The disease or disorder being studied or sign or symptom associated with the disease or disorder unless more severe than expected for the subject's condition.
- Overdose of either study drug or concurrent medication without any signs or symptoms.
- Symptoms associated with AD that are consistent with the subject's usual clinical course unless the symptom(s) meet(s) the criteria for "serious."
- Pregnancy.

8.1.2 DEFINITION OF SERIOUS ADVERSE EVENTS (SAE)

A serious adverse event (experience) or reaction is an untoward medical occurrence that, at any dose, fulfills one or more of the following criteria:

- a. Results in death (i.e., the AE actually causes or leads to death).
- b. Is life-threatening.

- An AE is considered “life-threatening” if, in the view of either the investigator or Sponsor, its occurrence places the patient or subject at immediate risk of death; it does not include AEs which, had it occurred in a more severe form, might have caused death.
- c. Results in inpatient hospitalization or prolongation of existing hospitalization.
 - Hospitalization for elective treatment of a pre-existing condition that did not worsen during the study is not considered an AE.
 - Complications that occur during hospitalization are AEs; if a complication prolongs hospitalization, the event is an SAE.
 - “Inpatient” hospitalization means the subject has been formally admitted to a hospital for medical reasons that may or may not be overnight; it does not include presentation at a casualty or emergency room unless the event meets the definition of an Important Medical Event (in the opinion of the Investigator or Sponsor).
- d. Results in persistent or significant incapacity or substantial disruption of the ability to conduct normal life functions.
 - The term ‘disability’ means a substantial disruption of a person’s ability to conduct normal life functions; this definition is not intended to include experiences of relatively minor medical significance such as uncomplicated headache, nausea, vomiting, diarrhea, influenza, accidental trauma (i.e., sprained ankle) that may interfere or prevent everyday life functions but do not constitute a substantial disruption.
- e. Results in a congenital anomaly in the offspring of a subject who received drug.
- f. Results in an Important Medical Event. Important Medical Events are events that may not result in death, be life-threatening, or require hospitalization but may be considered an SAE when, based upon appropriate medical judgment, they may jeopardize the subject and may require medical or surgical intervention to prevent one of the outcomes listed in this definition; examples of such medical events include allergic bronchospasm requiring intensive treatment in an emergency room or at home, blood dyscrasias or convulsions that do not result in inpatient hospitalization, or the development of drug dependency or drug abuse.
 - Medical and scientific judgment should be used in deciding whether prompt reporting is appropriate in this situation.

Note: if either the investigator or the Sponsor believes that the event is serious, the event must be considered serious and evaluated for expedited reporting.

Note: the terms “severe” and “serious” are not synonymous. Severity (or intensity) refers to the grade of an AE. “Serious” is a regulatory definition.

8.2 CLASSIFICATION OF AN ADVERSE EVENT

8.2.1 SEVERITY OF EVENT

Each AE or suspected adverse reaction must be assessed for its seriousness and severity. Severity will be assessed by the investigator or designee using the following definitions:

SEVERITY	DEFINITION
MILD	Aware of sign or symptom, but easily tolerated.
MODERATE	Discomfort enough to cause interference with usual activity.
SEVERE	Incapacitating with inability to work or do usual activity.

Outcome will be assessed using the following categories: recovered/resolved, not recovered/ not resolved, recovered/resolved with sequelae, fatal, or unknown.

8.2.2 RELATIONSHIP TO STUDY AGENT

Investigators are required to assess the causal relationship (i.e., whether there is reasonable possibility that the study drug caused the event) using the following definitions:

- Unrelated: another cause of the AE is more plausible; a temporal sequence cannot be established with the onset of the AE and administration of the study agent; or a causal relationship is considered biologically implausible.
- Possibly Related: There is a clinically plausible time sequence between onset of the AE and administration of the study agent, but the AE could also be attributed to concurrent or underlying disease, or the use of other drugs or procedures. Possibly related should be used when the study agent is one or several biologically plausible AE causes.
- Definitely Related: The AE is clearly related to use of the study agent.

If either the investigator or the Sponsor considers the event related, then the event will be considered related for reporting purposes.

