8.2.3 EXPECTEDNESS

The Sponsor or designee will be responsible for determining whether an AE is expected or unexpected. An AE will be considered unexpected if the nature, severity, or frequency of the event is not consistent with the Reference Safety Information described in the Investigator's Brochure.

For example, under this definition, hepatic necrosis would be unexpected (by virtue of greater severity) if the investigator brochure referred only to elevated hepatic enzymes or hepatitis. Similarly, cerebral thromboembolism and cerebral vasculitis would be unexpected (by virtue of greater specificity) if the Investigator's Brochure listed only cerebral vascular accidents. "Unexpected" as used in this definition, also refers to AEs or suspected adverse reactions that are mentioned in the Investigator's Brochure as occurring with a class of drugs or as anticipated from the pharmacological properties of the drug but are not specifically mentioned as occurring with the particular drug under investigation. For example, although angioedema is anticipated to occur in some patients exposed to drugs in the angiotensin-converting enzyme (ACE) inhibitor class and angioedema would be described in the Investigator's Brochure as a class effect, the first case of angioedema observed with the drug under investigation should be considered unexpected for reporting purposes ([FDA 2012](#)).

This definition of "unexpected" relies entirely on the Reference Safety Information in the Investigator's Brochure as the basis for determining if newly acquired information generated from clinical trials or reported

from other sources is unexpected. The suspected adverse reactions listed in the Investigator's Brochure (i.e., "expected") are those observed with the investigational drug and for which a causal relationship between the event and the drug is suspected or confirmed.

Sponsor assessment of expectedness and relationship to study drug/causality will determine the need for expedited reporting of AEs.

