8.5 STUDY HALTING RULES

If any of the following safety events occur, a Safety Evaluation Meeting (defined below) will be triggered:

- Three or more SAEs in the same system/organ/class (SOC) that are assessed as possibly or definitely related to the study agent (see [Section 8.2.2 Relationship to Study Agent](#)).
- An overall pattern of symptomatic, clinical, or laboratory events associated with the study agent that the Sponsor's Program Physician or designee consider a serious potential safety concern (e.g., suspicious overall pattern).

Events that are more likely related to the infusion procedure, such as infiltration or hematoma, will not be considered "drug related" and will not contribute to the count of definitely-related SAEs that would trigger a Safety Evaluation Meeting.

Safety Evaluation Meeting

If safety events of potential concern occur during the trial (i.e., 3 related events in the same SOC or a suspicious overall pattern, as defined above), a Safety Evaluation Meeting will be triggered, and dosing may be temporarily halted based on the observations. The Sponsor will inform investigators and the FDA in the event of any temporary halt in dosing at any time during the conduct of the study. The purpose of the meeting is for investigators, the Sponsor, and the CRO Medical Monitor to discuss and evaluate the safety of the subjects using available aggregated safety data and without compromising study blinding, unless the Sponsor deems unblinding necessary for safety evaluation.

Attendants at the Safety Evaluation Meeting will include the Program Physician of Alkahest (or his/her designee), the CRO Medical Monitor, and available active investigators participating in the trial. After sufficient data review, the Sponsor will choose one of the following courses of action:

1. Continue dosing with no change to protocol.
2. Halt dosing in all groups and stop the study.
3. Continue with a modified protocol design and amend the protocol as appropriate.

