6.1.4 Analysis Methods

There will be no formal statistical testing unless indicated otherwise.

A summary will be provided for the following TEAEs overall (Table 14.3.1.1):

- Subjects with Any TEAE
- Subjects with Any Study Drug-Related TEAE
- Subjects with Any TEAE with an Outcome of Death
- Subjects with Any Serious TEAE
- Subjects with Any Study Drug-Related Serious TEAE
- Subjects with Any TEAE Leading to Discontinuation of Study Drug
- Subjects with Any Study Drug-Related TEAE Leading to Discontinuation of Study Drug
- Subjects with Any TEAE of Special Interest
- Subjects with Any Study Drug-Related TEAE of Special Interest

The adverse events will be shown by MedDRA system organ class and preferred term, in order of descending overall frequency. For each AE, the percentage of subjects who experience at least 1 occurrence of the given event will be

summarized. Incidence tabulations will be provided for overall summary (Table 14.3.1.2.1-14.3.1.2.2), summary by highest severity (Table 14.3.1.3), and summary by relatedness (Table 14.3.1.4).

Incidence of Serious TEAEs, TEAEs of Special Interest, TEAEs Leading to Subject Withdrawal and TEAEs Leading to Death will be tabulated by MedDRA System Organ Class and Preferred Term (Table 14.3.1.5.1-14.3.1.5.4) and listed as well (Listing 14.3.1.6.1-14.3.1.6.4).

Adverse events with preferred terms associated with blood pressure changes will also be presented by infusion period, SOC, PT, and treatment group. Infusion period will be further categorized by whether the event start date occurred during the infusion period or after the infusion period. Examples of such events can be identified by the following preferred terms: blood pressure decreased, blood pressure diastolic decreased, blood pressure systolic decreased, blood pressure increased, increased blood pressure, blood pressure diastolic increased, blood pressure systolic increased, hypotension, hypertension, low blood pressure, high blood pressure. This is a non-exhaustive list and a review of AE MedDRA coding will be conducted prior to lock to identify all events associated with blood pressure changes (Table 14.3.1.5.5.).

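### Protocol 8.2.2 lets one adverse event meet both Unrelated and Possibly Related, with no rule for which applies, so related counts depend on the line the investigator reads

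*Protocol*

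**What the plan says.** Protocol 8.2.2 has investigators judge causality by asking "whether there is reasonable possibility that the study drug caused the event". It then defines three categories.

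- **Unrelated** is a list of alternatives. It begins "Unrelated: another cause of the AE is more plausible", continues with a timing clause, and ends "or a causal relationship is considered biologically implausible". Because the items are joined by *or*, any one of them is enough.
- **Possibly Related** needs a plausible time sequence and accepts that disease, other drugs or procedures might also explain the event. It adds an instruction: "Possibly related should be used when the study agent is one or several biologically plausible AE causes".
- **Definitely Related** is for events clearly due to the agent.

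The section closes with a rule that an event is related for reporting purposes if either the investigator or the Sponsor thinks so.

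The label is used in two places. Protocol 8.5 calls a Safety Evaluation Meeting when three or more serious events in one system organ class are "assessed as possibly or definitely related to the study agent", and it refers back to 8.2.2 for the meaning. SAP 6.1.3 carries the three levels forward, and SAP 6.1.4 tabulates rows such as "Subjects with Any Study Drug-Related TEAE" without saying which levels count as related.

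**The concern.** Unrelated turns on how the agent ranks against another cause. Possibly Related turns on whether the agent is a plausible cause at all. These are different questions, so one event can satisfy both. Possibly Related puts no limit on how plausible the alternative may be, and nothing says which category wins.

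The first ground for Unrelated also conflicts with the section's standard. There can be a reasonable possibility that the drug caused an event even when something else is the likelier cause.

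Two things are at stake. One is consistency: up to four sites could label the same kind of event differently while each follows the protocol. The other is the set of outputs that use the label, namely the count-based trigger in 8.5 and the relatedness tables.

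**Working it through.** The plan gives no figure on this point to reproduce, so the check is to enumerate the definitions.

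**Step 1: the definitions as a truth table.** Take three yes/no attributes from 8.2.2: timing plausible (T), another cause more plausible (M), agent biologically plausible (B).

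- Unrelated = M, or not T, or not B.
- Possibly Related = T and B, taking some other attribution to be available.

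| T | M | B | Unrelated | Possibly Related |
|---|---|---|---|---|
| yes | yes | yes | **yes** | **yes** |
| yes | yes | no | yes | no |
| yes | no | yes | no | yes |
| yes | no | no | yes | no |
| no | yes | yes | yes | no |
| no | yes | no | yes | no |
| no | no | yes | yes | no |
| no | no | no | yes | no |

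One of the eight combinations meets both definitions; the other seven meet exactly one. The other three rows with M = yes are already Unrelated on timing or biology. So on this coding the first ground for Unrelated decides the outcome only in the row where it collides with Possibly Related.

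**Step 2: the trigger in 8.5.** Suppose three serious events in one system organ class all fall in the overlapping row.

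- All read as Unrelated: count = 0, below the threshold of 3, trigger not met.
- All read as Possibly Related: count = 3, trigger met.

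**Step 3: the tables.** SAP 6.1.4 lists nine rows for Table 14.3.1.1. Four are restricted to study drug-related events: any, serious, leading to discontinuation of study drug, and of special interest. Table 14.3.1.4 is wholly by relationship.

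For scale, assume 20 subjects at 2:1 split as 13 and 7. One subject whose only event is in the overlapping row moves the any-related row by 1/13 = 7.7 percentage points in the GRF6019 arm, or 1/7 = 14.3 points in the placebo arm.

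**Step 4: rules that might settle it.**

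- The either-party rule in 8.2.2 is limited to reporting purposes. Neither document extends it to the 8.5 count or the SAP tables.
- The strongest-attribution rule in Protocol 10.4.2 covers repeat reports of the same event in one subject. It does not classify a single ambiguous event.
- The carve-out in 8.5 for events more likely due to the infusion procedure does set a precedence, but only for the procedure. Underlying disease and other drugs have no counterpart.

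**The case against.** The best defence is that 8.2.2 can be read coherently. It opens with the reasonable-possibility standard, and only Possibly Related carries a usage instruction, so the disputed event belongs there. That is a sensible reading, and the fix should follow it. But the text does not say the instruction overrides the first ground for Unrelated, and on that reading the ground has no work left to do. An investigator who applies it literally is still following the protocol.

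The second defence is that little harm follows, and much of this stands. The 8.5 count calls a meeting and does not itself stop dosing. The other 8.5 trigger, an overall pattern of concern, is a matter of judgment and needs no count of causality categories. Protocol 8.4.2.1 sends every serious event in within 24 hours whatever its label, so a cluster would still be seen. SAP section 3 adds ongoing safety assessment. The primary endpoint is all-cause incidence, and adverse events have no formal testing. Safety is assessed by blinded personnel, so the ambiguity is not expected to favour an arm. It still affects the counts.

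A reader might infer more than the documents support:

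- *That nearly every event in this population is ambiguous, so the related rows could end up empty.* The overlap needs an alternative that is more plausible, not merely present. No frequency is given, and Protocol 8.1.1 already excludes usual-course AD symptoms unless serious.
- *That a probability of missing the trigger can be quoted.* That needs the number of ambiguous serious events and the chance of each label, and the documents give neither.
- *That 8.2.3 contradicts the either-party rule.* It says "Sponsor assessment of expectedness and relationship to study drug/causality will determine the need for expedited reporting of AEs", but the Sponsor can apply the either-party rule in making that assessment. Protocol 8.4.2.2 notes that the site's causality judgment may affect expedited reporting.

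**Conclusion.** The overlap is real and follows from the wording alone: one of eight attribute combinations meets both definitions, with no rule to choose between them. The first ground for Unrelated also conflicts with the section's own standard.

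The practical reach is moderate. The label decides whether three overlapping serious events in one class count as 0 or 3 toward the count-based trigger, and it feeds four of nine rows of Table 14.3.1.1 and all of Table 14.3.1.4. It does not affect all-cause incidence, the overall-pattern trigger or the 24-hour reporting of serious events. The 7.7 and 14.3 point shifts assume a 13/7 split and are illustrations only. How often the overlap would arise cannot be worked out from the documents. It should be corrected because the correction is small and safety is the primary objective; it does not show that safety oversight would fail.

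**What to change.** Reconcile the Unrelated and Possibly Related definitions in Protocol 8.2.2 so that they are mutually exclusive and agree with the reasonable-possibility standard and the existing usage instruction. One way is to limit the first ground for Unrelated to events where another cause explains the event and the agent is not a plausible contributor. In the table above, the overlapping row then becomes Possibly Related only, and the number of combinations meeting both definitions falls from 1 to 0. The threshold in 8.5 need not change.

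In SAP 6.1.4, state that study drug-related means Possibly or Definitely Related, which matches the grouping in 8.5.

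The cost is a sentence or two in the protocol, one in the SAP and a memo to sites; the revision history shows that clarification memos have been used twice before. The downside is that somewhat more events will be called possibly related.
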